4.3 Study Recruitment and Enrollment Procedures

Potential participants will be identified in three ways: (1) postcard mailings and invitation letters; (2) physician referrals and IRB approved chart screening; and (3) flyers, advertisements and press releases

Physician referrals will come primarily from cancer centers at University of Michigan Cancer Center Breast Clinic in Ann Arbor, MI, and the Baylor Scott & White Health Center in Waco, TX.

At Michigan, key eligibility criteria will be used to identify potentially eligible women through the Data Office for Clinical and Translational Research (formerly the Honest Broker Office) and

Electronic Medical Record Search Engine (EMERSE). EMERSE (Electronic Medical Record Search Engine) provides a self-service web-based tool for authorized users to search clinical notes from our electronic medical record (CareWeb and Michart). Users can input their own terms or phrases and get results within seconds. The clinical notes include admission, discharge, and progress notes, as well as ambulatory care notes and notes from radiology, pathology, and other reports going back to 1998. With EMERSE, users can input a list of medical record numbers and search across that set, or can find a list of patients who have the term(s) of interest if it is not yet known who they are." Charts will be further screened, with IRB approval, for eligibility. If eligible, women will be sent an invitation letter where they can opt in or out of being contacted to learn more about the study. In addition, at Michigan, outreach will occur through obstetrics and gynecology, mammography, and internal medicine clinics to enable recruitment of women without a history of breast cancer. Mass mailings and local advertisement may also be used.

At Baylor University, a successful and proven method of accrual has been the use of mass mailings, local advertisement (e.g., newspaper, magazines, flyers). Additionally, [name] is a medical associate with Baylor Scott & White Health Center, which provides a direct connection with physicians and medical staff who will provide potential referrals.

These research teams have a proven past in successful accrual for multiple research studies using similar recruitment techniques.

The targeted population for this study are women who wish to avoid hormonal therapy to treat hot flashes. Women who have gone through natural menopausal transition and those with a history of breast cancer will be included.

Those who are interested in participating in the study will be able to express their interest in doing so via phone, email, or text messaging. Research personnel will then correspond with these interested individuals via phone, email, or text messaging, to schedule a phone screening appointment.

During the phone screening appointment, more study details are provided. If the individual is still interested in participating after this information is provided, verbal consent will be obtained and potential eligibility will be determined using the Inclusion/Exclusion Criteria Screening Checklist which outlines the criteria listed in Sections 4.1 and 4.2. If a woman appears to be eligible, she will be scheduled for a baseline visit (conducted via telephone or video conference during COVID-19 restrictions) where the informed consent process for study procedures, the study purpose, procedures and requirements for baseline data collection will be explained. If she is interested in participating, she will sign the IRB-approved consent form to begin baseline data collection and be assigned a participant study ID number and will be considered enrolled in the study. If the baseline visit is conducted by telephone or video conference, the IRB-approved consent form will either be sent to the participant with a postage-paid envelope for return to the study team or sent through a secure, online platform. The online platform that will be utilized for this study will be DocuSign.

A Screening and Enrollment Log will be maintained at both sites to document eligibility/ineligibility, screen & consent dates, and referral source of each individual screened.

Once baseline data have been collected, a randomization/education visit (conducted by phone or video conference during COVID-19 restrictions) will be scheduled.

Eligible participants will be randomized to either self-administered hypnosis or self-administered sham white noise hypnosis. Randomization and mailing of appropriate intervention materials will take place several days before the visit if the visit is to take place through phone or video conference due to COVID-19 restrictions. Participants will also have an option of having the appropriate intervention materials shared with them electronically. Education about implementing their assigned arm will take place and for those assigned to hypnosis, the hypnotizability scale will be administered. However, the hypnotizability scale will not be administered if the randomization visit takes place through phone or video conference due to COVID-19 restrictions. Randomization will be

accomplished by the development of equally distributed tables of random numbers by the statistical team.

It is expected that each site (Baylor University and University of MI) will each recruit approximately half of the participants. Accrual will be closely monitored and efforts to randomize an equal number at each site will be made (see Section 9.4). Should accrual and randomization at either site significantly exceed 50% then the accrual percentage will be reduced at the other site accordingly. The randomization list will be kept by the study statistician.

5. STUDY INTERVENTIONS

5.1 Interventions, Administration, and Duration

5.1.1 Self-Administered Hypnosis Intervention

Participants in the self-administered hypnosis intervention group will be given booklets on the use of hypnosis for the treatment of hot flashes; and be provided with accompanying audio recordings containing hypnosis inductions as described above in Table 3. The booklets provide patient-education about hot flashes and treatment options, and include weekly instructions for a six-week long structured self-administered hypnosis intervention program for the treatment of hot flashes. A one-week baseline period will include the daily hot flash diary completion for the baseline week. During the baseline week, participants will also collect the physiologic measures, saliva three times per day over two consecutive days, and correspondingly, wearing the HRV monitor for 24 hours one day and for two 6 minute supine recordings on the other day. The physiologic measures will be optional for participants using phone or video conference for the baseline visit due to COVID-19 restrictions. Participants will then be asked to listen to audio-recordings of hypnosis inductions designed for the treatment of hot flashes, daily throughout 6 weeks. Each recording will be about 20 minutes long. Practices using the recordings will be documented on the Hypnosis Practice Log.

5.1.2 Self-Administered Sham White Noise Comparator

This group will serve as the control arm, but this hypothesis will be blinded to participants such that both arms will be introduced as self-administered hypnosis programs. This is a true statement that will avoid bias on the part of participants who may feel "cheated" if randomized to a control condition and could therefore bias the results. This arm has been developed to account for placebo and non-specific effects inherent in symptom management trials. Similar to the hypnosis group, this group will have a one-week baseline period that will include the daily hot flash diary completion for the baseline week. During the baseline week, participants will also collect the physiologic measures, saliva three times per day over two consecutive days, and correspondingly, wearing the HRV monitor for 24 hours one day and for two 6 minute supine recordings on the other day. The physiologic measures will be optional for participants using phone or video conference for the baseline visit due to COVID-19 restrictions. Participants will be given booklets with the same basic information on hot flashes, which includes education on the treatment options for hot flashes. This set of booklets will also be accompanied by an audio

recording that contains information about hot flashes, and a 20-minute audio-recording of white noise. These audio-recordings provide no hypnotic induction, no guided relaxation, nor hypnotherapy. Participants will complete the baseline questionnaires at the baseline visit, with the exception of the hot flash daily diary which will be completed daily during the baseline week as in the hypnosis arm. Then participants will have a visit that will educate them about their randomized treatment and they will be asked to listen to their assigned audio recording daily for 6 weeks.

This control condition is identical to that used in both [name] and [name] previous research and matches the time, attention and modalities used in the hypnosis group. [39, 41] Participants were very satisfied with this arm in previous trials, had equal adherence as the hypnosis group and yet this arm yielded placebo effects equal to those obtained through a placebo pill in antidepressant trials. Participants assigned to this group will also be asked to listen to the audio recordings, focusing their attention in any way they feel would be helpful for reducing their hot flashes, and document their "practices" on the Hypnosis Practice Log.

This is an active control arm, accounting for all of the components in the intervention arm but lacking the mechanistic therapeutic approach and in previous research was shown to provide the same hot flash reduction as the placebo arm in other trials.^[37, 74]

5.2 Handling of Study Interventions

Participants in both groups will be scheduled to receive phone calls from a research assistant approximately every 10 days, for a total of 5 phone calls during the six-week study period (see Table 2). The first phone call will be scheduled approximately 7 days after the randomization/education appointment. This call is intended to make sure the participant understands their assigned treatment. An additional phone call will be made during week 11 to remind the participant of the week 12 data collection.

All phone calls will be scripted and structured to allow research staff/participant-contact at scheduled intervals and may be as brief as a voice-mail left by the research staff providing call-back information to several minutes spent discussing general topics outlined on the Phone Call Checklist & Research Contact Staff Notes form. Research contact staff will document the calls using this form and participants will be encouraged to maintain and use the program materials; but there will be no therapeutic intervention during the call.

The delivery of the self-administered hypnosis intervention and the self-administered sham white noise hypnosis outlined in detail for both groups of the study in the Research Standardized Intervention Delivery Manual. Information regarding overall study procedures are detailed in the Manual of Procedures (MOP).

5.3 Concomitant Interventions

Concomitant interventions specifically for hot flashes are not allowed (see 4.1 and 4.2).

5.3.1 Allowed Interventions

Antidepressant use is allowed on study if the antidepressant has been for at least 2 months with no plans to change dose or antidepressant during this study and the participant meets the eligibility criteria of at least 4 hot flashes per day or 28 per week. Vitamin E is allowed. Any other treatments, if not used specifically for hot flashes, and participant meets hot flash frequency criteria, are allowed.

5.3.2 Required Interventions

None

5.3.3 Prohibited Interventions

See 5.3 and Inclusion/Exclusion Criteria (4.1 and 4.2)

5.4 Adherence Assessment

Adherence will be assessed through the frequency of at-home practice. Participants will complete the Self-Hypnosis Practice Log each day beginning at Week 1 and for the duration of their participation time in the study.

6. STUDY PROCEDURES

Schedule of Activities 6.1

Table 4: Schedule of Activities	Enrollmen	BL wk	Treatment and Follow-up in weeks						
	1 2 3		3	3 4 5		6 12			
Screening Checklist including PHQ-4	Х								
Informed Consent	X								
Demographic Questionnaire & Health History Intake		Х							
Aim 1 (primary outcome)									
Hot flash daily diary		D	D	D	D	D	D	D	D
Aim 2 (secondary outcomes)									
Hot Flash Related Daily Interference Scale		Х						Х	Х
PROMIS Emotional Distress- Anxiety Scale		Х						Х	Х
Pittsburgh Sleep Quality Index		Х						Х	Х
Global Impression of change								Х	
Aim 3 (mediators and moderators)									
Saliva collection for diurnal cortisol*		Х						Х	
HRV through Polar V800**		Х						Х	
[name] Hypnotizability Scale (only hypnosis group)		X***							
Frequency of home practice			D	D	D	D	D	D	D
Check In Phone Calls			Х	Х	Х	Х	Х	†	1

6.2 **Description of Evaluations**

The Schedule of Measures (**Table 4**) defines what is to be done at each week of the study period, which is approximately 13 weeks.

It is divided primarily by the type of evaluation (i.e.; Enrollment, Baseline, and Treatment & Follow-up). The Treatment & Follow-up period is further divided by study weeks.

6.2.1 Screening Evaluation

Inclusion/Exclusion Criteria Screening Checklist

This brief evaluation may be conducted over the phone and occurs to establish probable eligibility for the study. Questions are asked to confirm that the candidate meets the inclusion/exclusion criteria for the study, using a YES/NO format, and the 4-item PHQ-4 brief screening tool.

The PHO-4 will be completed to assess exclusionary criteria of a PHO-4 score > 9. This brief screening measure was developed from the PHQ-9 and GAD-7 to be an ultra-brief screening tool for depression and anxiety disorders.^[80] It has been validated in the general population and found to be comparable to the PHO-8. [81] Scores on the PHO-4 range from 0 to 12, with scores 0-2 being normal; 3-5 indicating mild symptoms; 6-8 moderate symptoms; and 9-12 severe. Cronbach's alpha for the 4 items was 0.85. The PHQ-4 was strongly correlated with the mental health subscale of the SF 20 (r=.80) and social functioning (r=.52). These correlation coefficients were nearly identical to those of the PHO-8. [80]

samples will be collected over 2 days, upon awakening, 30 minutes later and a bedtime (around 10 pm); Note: this will be optional during* COVID-19 restrictions

^{**}data will be collected during the same two days as cortisol sample collection; Note: this will be optional during COVID-19 restrictions

^{*}EHS will be done during randomization/education visit; Note: EHS-CF will be administered if visit is by telephone or video conference

Individuals scoring ≥9 on the PHQ-4 will be provided with additional referral information. At the University of Michigan, a referral will be made to psychology or psychiatry and the participant's oncologist will be notified, if applicable. There is also an oncall psychiatrist available Monday through Friday from 8 a.m. to 5 p.m. to assist with crisis situations. After hours, an on-call consultant can be reached by calling the clinic operator and arrangements can then be made to have the patient seen in the Emergency Room if necessary by the on-call psychiatrist. At Baylor University, a referral will be made to the Baylor Psychology Clinic (which is open Monday through Friday from 8 a.m. to 7:30 p.m.), Baylor Scott and White Health Center, or community medical health services. After hours, participants will be referred to the Emergency Room at Baylor Scott and White Health Center. (See Section 7.2).

Following an initial screen on the Inclusion/Exclusion Criteria Screening Checklist, participant candidates who meet the criteria from this checklist interview will be scheduled to attend the baseline appointment, where they will be asked to sign an informed consent form (ICF) prior to educational information about the study and/or baseline measures completion.

6.2.1.1 Consenting Procedure

There will be two consenting processes; one verbal consent process for the screening and a written informed consent process for study procedures.

Screening Verbal Consent

Research staff, not involved with study intervention will ask for verbal consent prior to completing the Inclusion/Exclusion Criteria Screening Checklist, using an IRB approved script either in person or over the phone with the candidate which states:

"Hello. My name is _____ and I am speaking with you in regard to a clinical trial involving the use of two different self-administered hypnosis programs for hot flashes that we are conducting at (Baylor University/University of Michigan). In order to complete the Inclusion/Exclusion Screening Checklist to assess your potential eligibility in this study, I will need to ask for your consent to participate to the screening process, which involves me asking and you answering questions that are all related to the criteria established to determine eligibility for participation in this study. The total time for the completion of this screening process is approximately 15 minutes.... Script is included in recruitment materials.

Individuals who respond with "NO" will be thanked for their time and the questions from the Inclusion/Exclusion Criteria Screening Checklist will not be asked.

The individual's response will be indicated by circling "YES" or "NO" on the script page and the screener will sign the form. These consent forms will be maintained with the Screening and Enrollment Log.

Written Informed Consent for Study Procedures

Research staff not involved with the study intervention will complete the informed consent process prior to beginning any study procedures.

Informed consent is a process that is initiated prior to the individual agreeing to participate in the study and continues throughout study participation. An IRB-approved, signed informed consent form (ICF) describing in detail the study procedures, risks/benefits, and participant rights will be given to the individual to follow during the consent process. The investigator or research staff will explain the research study to the participant using a standardized presentation format (e.g., PowerPoint presentation, written script), which will comprehensively cover all information in the ICF.

The individual will be encouraged to read through the document, or if requested, the ICF will be read aloud in its entirety. The individual may take the ICF to discuss with outside parties (e.g., spouse, friend, physician), or think about it prior to agreeing to participate, and have an opportunity to ask questions about the study. This informed consent form will include an addendum that addresses IRB-approved modes of communication throughout study participation (i.e., use of text messaging and email for scheduling purposes only). Once the ICF is signed by the participant and the person who explained the research study, the individual will be given a copy of the document, assigned a Study ID, and considered a participant in the study. Participants may withdraw consent at any time throughout the course of the study.

The consent process will be documented on the Data Collection Quality Control Form (DCQCF): Informed Consent and the signed original ICF will be filed separately from participant charts in a locked file drawer.

To complete the informed consent process at the end of study participation, study staff will inform the participant when his/her participation has come to an end and will document the discussion on the Data Collection Quality Control Form: Study Completion.

6.2.1.2 Screening

Screening is to identify eligible participants and will be completed during the completion

of the Inclusion/Exclusion Criteria Screening Checklist, after which individuals may be scheduled at any time to begin study participation, with the following exception:

• If at screening, the individual self-reports the use of other putative therapies for hot flashes for at least one month prior to enrollment, then a washout period of one month will be required prior to the scheduling of the baseline appointment.

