4. SELECTION AND ENROLLMENT OF PARTICIPANTS

4.1 Inclusion Criteria

Participants must meet all inclusion criteria to participate in this study.
Postmenopausal as defined by one of the following criteria:

- 1) no menstrual period in the past 12 months
- 2) chemical menopause (LHRH antagonists)
- 3) surgical menopause (bilateral oophorectomy)
- 4) evidence of menopause status per FSH and estradiol levels per institutional guidelines.
- Self-reported history of a minimum of 4 hot flashes per day or 28 hot flashes per week at baseline
- Age over 18 years and able to give consent for participation in the study
- Participants on antidepressants for hot flashes are allowed on study if the antidepressant has been for at least 2 months, there are no plans to change the dose or antidepressant, and the number of hot flashes meets the eligibility criteria of at least 4 hot flashes per day or 28 per week.
- Have discontinued other putative therapies for hot flashes for at least one month prior to enrollment (Vitamin E will be allowed)
- Women with a diagnosis of DCIS or invasive breast cancer stages 0-III are allowed to participate and may be on endocrine therapy of any kind. If on endocrine therapy, women must be on endocrine therapy for 4 weeks and not expected to stop endocrine therapy during the study. If not on endocrine therapy, participants should not be planning to start during the course of the study. However, unexpected treatment with endocrine therapy will not require study withdrawal but will be recorded and considered in the analysis.

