6.2.2 Enrollment, Baseline, and/or Randomization

6.2.2.1 Enrollment

Once the candidate has met screening eligibility criteria, and signed the written ICF for study procedures, she will be considered enrolled in the study. Her enrollment date will be the date she signs the ICF. The participant's enrollment date will be recorded on the Enrollment Log. Participants will be enrolled during months 10-47 of the study. Not all participants who enroll will progress to randomization (due to screen failures and those who actively withdraw from the study), we anticipate enrolling individuals as needed at Baylor University to achieve our randomization goal of 131 participants randomized.

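### A one-month washout that the study requires comes before the written consent form is explained and signed.

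*Combined protocol and SAP*

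**What the plan says.** All references are to the combined protocol and SAP.

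- **Washout.** Section 6.2.1.2 lets eligible women be scheduled at any time, with one exception. If a woman reports other putative hot-flash therapies at screening, "then a washout period of one month will be required prior to the scheduling of the baseline appointment".
- **Eligibility clock.** Section 4.1 requires women to "Have discontinued other putative therapies for hot flashes for at least one month prior to enrollment". Vitamin E and stable antidepressants may continue, and Section 4.2 spares therapies taken for other reasons.
- **Where written consent happens.** Section 4.3 describes the baseline visit as the one "where the informed consent process for study procedures, the study purpose, procedures and requirements for baseline data collection will be explained". Section 6.2.1 says the same of candidates at this visit, "where they will be asked to sign an informed consent form (ICF) prior to educational information about the study and/or baseline measures completion". Mail and DocuSign are offered for remote visits only: "If the baseline visit is conducted by telephone or video conference, the IRB-approved consent form will either be sent to the participant" by post or through the online platform.
- **Enrollment date.** Section 6.2.2.1: "Once the candidate has met screening eligibility criteria, and signed the written ICF for study procedures, she will be considered enrolled in the study". The same section fixes the date: "Her enrollment date will be the date she signs the ICF".
- **Time to reflect.** Section 6.2.1.1: "The individual may take the ICF to discuss with outside parties (e.g., spouse, friend, physician), or think about it prior to agreeing to participate".
- **Two consents.** Section 6.2.1.1 provides a verbal consent for screening and a written one for study procedures. The written process is to be finished before any study procedure starts. The verbal script is shown only in part. That part asks for consent to answer eligibility questions, for about 15 minutes.

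**The concern.** The study makes a treatment change a condition of entry, and the woman makes that change before she reaches the visit at which the procedures, risks and rights are set out in writing. The chance to take the form to a physician is most useful before a therapy is stopped, and on the planned order it comes afterwards.

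The therapy need not be trivial. Section 2.2 names gabapentin as a common non-hormonal alternative for hot flashes, and the exemptions in Sections 4.1 and 4.2 do not cover gabapentin taken for hot flashes. A prescribed drug can therefore fall under the washout.

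What is at stake is participant protection through the order of steps. The estimate of the treatment effect is not in question.

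**Working it through.** The plan gives no figure to reproduce, so the check sets the sections side by side and asks whether any permitted order puts the signature first.

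**Inputs**
- S = date the other therapy is stopped.
- E = enrollment date.
- C = date the ICF is signed.
- B = date of the baseline visit.

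**Steps**
1. Section 4.1: the therapy must have been stopped at least one month before enrollment, so E − S ≥ 1 month.
2. Section 6.2.2.1: enrollment is dated at the signature, so E = C.
3. Substituting, C − S ≥ 1 month. A current user who signs while still on the therapy fails the criterion on the day she signs. Stopping first is the only eligible order.
4. Section 6.2.1.2 gives the same order independently. The washout comes before the baseline appointment is even scheduled, and Sections 4.3 and 6.2.1 place the signature at that appointment, so C = B.
5. Section 6.2.2.3 confirms where the washout falls. It voids the verbal consent if more than 30 days pass between screening and the baseline appointment, but makes an exception for washout. So the washout lies between screening and baseline, and the women who change treatment are the ones excused from renewing the only consent they have given.

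**Resulting sequence:** verbal screening consent and checklist → washout of one month → baseline visit, where the ICF is explained and signed and enrollment is dated.

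**Minimum time off therapy before written consent**
- As written: C − S = 1 month.
- If the clock ran from the baseline visit (B − S ≥ 1 month) and the form were signed no later than the stop (C ≤ S): zero.

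The month off therapy before baseline is the same in both cases. Only the signature moves. The condition in Section 6.2.1.2 is awkwardly worded about which past use triggers a washout, but steps 1 to 3 do not depend on it.

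**The case against.** The best case for the plan has four parts.

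- **The protocol never calls the washout a study procedure.** The rule sits under the Screening heading, and Section 6.2.1.1 assigns verbal consent to screening. This stands as a limit. A reader might infer that the plan breaches its own rule on written consent, but that follows only if a required washout counts as a study procedure, and the documents do not settle it. The order of steps holds either way.
- **The script is cut off.** The rest is in the recruitment materials, Section 4.3 says that more details are given by phone before verbal consent, and the woman's answer is recorded and filed. This also stands. A reader might infer that women stop therapy uninformed, and the documents do not show that. A spoken explanation is still not the written form, and no section offers the form before the washout.
- **The chance to consult a physician remains open until she signs.** True for the decision to join. For the decision to stop therapy, the planned chance comes too late.
- **A line in the script, or an advance copy of the ICF, would be enough.** Either would help with information, and nothing in the plan forbids it. Neither would put the signature before the treatment change.

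A reader might also infer that washout women need a repeat PHQ-4, because it is scheduled only at screening. The documents do not support that. They show no effect of stopping these therapies on the score, and women without a washout can also be randomized weeks after their PHQ-4. Section 7.2 has severe or acute anxiety evaluated during the history intake, which is a baseline item (Sections 6.1 and 6.2.2.2) and so comes after the washout.

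**Conclusion.** The point holds as one about the order of consent. For a current user of another hot-flash therapy, the plan allows only one sequence, and in it a stop required by the study precedes the ICF signature by at least one month.

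It rests on two readings. The first is that enrollment in Section 4.1 means the date defined in Section 6.2.2.1. The second is that the woman stops because the study requires it, and not for reasons of her own.

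The documents do not say how many women would need a washout, and none is assumed. The point does not affect the sample size, the analysis or the primary estimate. Severity is minor. It is worth raising because the remedy is cheap.

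**What to change.** 1. Obtain the written ICF before any washout undertaken for the study, in person or by the mail or DocuSign route that Section 4.3 now describes only for remote baseline visits. Otherwise, document that the woman had already stopped for reasons unrelated to the trial.
2. In Section 4.1, count the month back from the baseline visit instead of from enrollment. This also fits Section 4.2, which applies the exclusions at baseline.
3. Align Sections 4.3, 6.2.1, 6.2.1.2, 6.2.2.1 and 6.2.2.3, so that the form may be signed before the baseline visit and before the washout criterion is met.
4. Section 6.2.2.3 now treats women who sign at baseline but do not return for randomization as screen failures to be replaced. Extend that rule to signers who do not complete the washout.

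**Cost.** Wording changes in six sections, one earlier consent contact for washout women only, and a few more enrolled women who never reach randomization. Section 6.2.2.1 already expects such losses. They fall before randomization, so the randomized sample is not affected.
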